#### 10.2.2 Infusion Related Reactions (IRR)

IRRs are those TEAEs which occur during the infusion or within 2 hours after the completion of the infusion and their causality is definitely, probably, or possibly related.

Classification rules for assignment of patients with TEAEs during the infusion or within 2 hours after the infusion are described below.

Injection site reactions with SOC and PT listed in Table 2 are not considered IRR and should be excluded from the IRR analysis.

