|---|---|------|----------------|----|----|----|----|----|----|----|----|-----|-----|-----|-----|-----|
| Activity /Visit Number/ Inf | S | V1 | 2w eek s | V2 | V3 | V4 | V5 | V6 | V7 | V8 | V9 | V10 | V11 | V12 | V13 | V14 |
| Quality of Life (5Q-5D-5L) | | x | | | | | | | x | | | | | | | x |
| Mainz Severity Score Index (MSSI) | | x | | | | | | | | | | | | | | x |
| Request patient approval by Medical Monitor | | x | | | | | | | | | | | | | | |
| Medical Monitor approval | | x | | | | | | | | | | | | | | |
| Echocardiography | | x | | | | | | | x | | | | | | | x |
| Cardiac function assessment (stress test) | | x | | | | | | | | | | | | | | x |
| Brain MRI | | x | | | | | | | | | | | | | | x |
| Adverse events assessments | | x | | x | x | x | x | x | x | x | x | x | x | x | x | x |
| Mutation analysis | | x | | | | | | | | | | | | | | |
| Con Meds | x | x | | x | x | x | x | x | x | x | x | x | x | x | x | x |
| Urine lyso Gb3 concentration | | x | | | x | | | x | | | | | x | | | x |
| Plasma Gb3 concentration ² | | x | | | x | | | x | | | | x | | | | x |
| Plasma Lyso Gb3 concentration ² | | x | | | x | | | x | | | | x | | | | x |
| Study Drug IV infusion ^{8,9} | | x | | x | x | x | x | x | x | x | x | x | x | x | x | x |
| Observe Patient ⁶ | | x | | x | x | x | x | x | x | x | x | x | x | x | x | x |
| Call Patient ⁷ | | x | | | | | | | | | | | | | | |

¹ Will be performed only for patients who have not had the test during the last 3 months before screening

² Will be performed pre-infusion

³ PK Time points: pre-infusion (baseline); 1 hour after the beginning of the infusion; at the end of the infusion, at 1 ± 0.25 , 2 ± 0.25 , 4 ± 0.25 , 8 ± 0.25 , 24 ± 0.5 , 48 ± 3 , and 96 ± 3 hours post-infusion and at 14 ± 3 , 21 ± 3 and 28 ± 3 days post-infusion

Patients who signed informed consent to this version (Version 4) before reaching Visit 7 (week 24), will perform PK at Visit 7; patients who signed informed consent after Visit 7 will perform PK at visit 11 (week 40).

⁵ Evaluate vital signs: blood pressure, pulse, temperature and respiration rate; any time pre-infusion, every 30 (±10) minutes during the first hour of the infusion, and from the second hour, 60 (±10) minutes up to the end of the clinical observation, and at the end of the observation time, if the patient tolerates the infusion. Otherwise, evaluate vital signs every 15 minutes until achieving tolerability.

⁶ According to [Appendix 8](#)

⁷ 24 hours post dosing first infusion

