The process for reducing observation time after the infusion will start after the attempt of tapering down the premedication was finalized (when one of the results could be the patient will remain on premedication). Until then, the post-infusion observation will be 4 hours.

On the next upcoming visit, the observation time will be reduced by 0.5 hour in each infusion up to 2 hours and then reduced to 1 hour post-infusion.

4. Referring the patient to home care set-up

The patients will be able to join the home care program once the patient is clinically stable with no additional changes in premedication, infusion rate, and observation time.

The changes require discussion and approval by the Medical Monitor/Director.

Table 2 represents a proposed regimen to achieve the goal of reducing premedication, infusion length, and post infusion observation; Other regimens need to be discussed and approved by the Medical Monitor/Director.

Table 2: Proposed Regimen of Reduced Premedication, Infusion Length, and Post-Infusion Observational Period

| Visit | | no premed up to 100 kg | single premed up to 100 kg | 2 premeds up to 100 kg | 3 premeds up to 100 kg | no premed more than 100 kg | single premed more than 100 kg | 2 premeds more than 100 kg | 3 premeds more than 100 kg |
|-------|------------------|------------------------|----------------------------|------------------------|------------------------|----------------------------|--------------------------------|----------------------------|----------------------------|
| | infusion time | 4.5 H | 4.5 H | 4.5 H | 4.5 H | 6 H | 6 H | 6 H | 6 H |
| | observation time | 4 H | 4 H | 4 H | 4 H | 4 H | 4 H | 4 H | 4 H |
| | premedication | no premed | same premed | same premed | same premed | no premed | same premed | same premed | same premed |
| 1 | home care option | NO | NO | NO | NO | NO | NO | NO | NO |
| | infusion time | 4 H | 4.5 H | 4.5 H | 4.5 H | 5.5 H | 6 H | 6 H | 6 H |
| | observation time | 4 H | 4 H | 4 H | 4 H | 4 H | 4 H | 4 H | 4 H |
| | premedication | no premed | remove premed | remove 1 premed | remove 1 premed | no premed | remove premed | remove 1 premed | remove 1 premed |
| 2 | home care option | NO | NO | NO | NO | NO | NO | NO | NO |
| | infusion time | 3.5 H | 4 H | 4.5 H | 4.5 H | 5 H | 5.5 H | 6 H | 6 H |
| | observation time | 3.5 H | 4 H | 4 H | 4 H | 4 H | 4 H | 4 H | 4 H |

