### **7.4 Multiple Comparisons**

No statistical tests are pre-planned in this study, which is mainly descriptive in nature and not powered for inferential analyses, hence, no adjustment for multiplicity is planned.

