**Table 2: Injection Site Reaction SOC and PT Not Considered as IRR**

MedDRA SOC	MedDRA Preferred Term
General disorders and administration site conditions	Infusion site discomfort Injection site discomfort Infusion site pain Injection site pain Infusion site hematoma Injection site hematoma
Injury poisoning and procedural complications	Contusion Procedural site reaction Procedural pain
Vascular disorders	Vein rupture

The number and percentage of patients with at least one IRR and the number of IRRs will be reported in an overall table with the following parameters: Any IRR; Mild or moderate IRRs; Severe IRRs; Serious IRRs; IRRs leading to withdrawal; IRRs leading to death.

This analysis will be repeated for the following sub-groups: ADA; Gender; Previous ERT; FD classification. An additional sub-group will be the location of administration (Home or Site).

IRR summary tables by SOC and PT will present the number and percentage of subjects with at least one IRR and the number of IRRs. The tables for the IRRs will be presented overall and by severity.

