#### **TEAE occurring during the infusion or within 2 hours after the infusion:**

To determine whether a TEAE occurred within this time frame, information collected in two CRF forms will be considered: AE form (fields of onset date and time) and Drug Administration form (fields of administration date; start and end times; question 1 “Did the patient experience an AE during or after the infusion?” and the sub-questions in case the answer is Yes. The sub-questions are 1a: “During the infusion”, 1b: “Within 2 hours after the infusion” or 1c: “Up to 24 hours after the infusion”). Events which meet one of the following criteria will be considered to occur during infusion or within 2 hours after the infusion:

- Date and time for both TEAE and infusion are complete, and the onset of the TEAE is during the infusion or within 2 hours from its completion (stop time), regardless of the answer to question 1 above;
- The answer to question 1 above is Yes, and the options selected are either 1a or 1b.

All other events will not be classified into this time category.

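### Infusion reactions are counted to 2 hours after infusion, but every home-permitted infusion in the proposed schedule has only 1 hour of observation, so the Home/Site summary has unequal detection

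*SAP*

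**What the plan says.** SAP 10.2.2 sets the time window: "IRRs are those TEAEs which occur during the infusion or within 2 hours after the completion of the infusion". Causality must also be definite, probable or possible. On reporting, the same section states: "The number and percentage of patients with at least one IRR and the number of IRRs will be reported in an overall table". It then repeats that summary by subgroup and adds location: "An additional sub-group will be the location of administration (Home or Site"). The output is Table 14.3.3.5.1.

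An event enters the window by one of two routes. The first is complete dates and times with "the onset of the TEAE is during the infusion or within 2 hours from its completion (stop time), regardless of the answer to question 1". The second is a tick on the Drug Administration form for during the infusion (1a) or for the 2 hours after it (1b). The form's later options read "1b: “Within 2 hours after the infusion” or 1c: “Up to 24 hours after the infusion". Events meeting neither rule are left out of the window.

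Protocol Appendix 8, item 3, starts observation at 4 hours; after premedication tapering, "the observation time will be reduced by 0.5 hour in each infusion up to 2 hours and then reduced to 1 hour post-infusion". Home care opens only when the patient is stable and no further changes in premedication, rate or observation are due (item 4). Table 2 of that appendix is described as a proposed regimen, and others are possible with approval. In the Study Flow Chart (protocol 9.1), vital signs run to the end of observation, and the only scheduled call is "24 hours post dosing first infusion".

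**The concern.** The counting window is the same at home and on site, but scheduled observation inside it is not. In the second hour after a home infusion nobody is scheduled to be watching, and vital signs are no longer taken. A fall in blood pressure without symptoms cannot be reported by the patient. A reaction that is felt must be mentioned later and then given a clock time or a 1b tick. No contact is scheduled between the end of home observation and the next 4-weekly visit. On site the second hour is more often covered.

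At stake is how Table 14.3.3.5.1 is read. A lower home figure could reflect less watching rather than fewer reactions. SAP section 12, item 8, also folds the hypersensitivity analysis into the IRR evaluation, so the same unevenness carries over to hypersensitivity by location.

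**Working it through.** The documents state no figure on this point, so there is nothing to reproduce. The check is a count of protocol Table 2: 14 visits x 8 weight-and-premedication columns = 112 cells. Each cell is classed as home-permitted (home option YES) or site (NO), and its observation time is read off.

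| Visit | Home-permitted cells (all 1 h) | Site cells | Site cells with 2 h or more |
|---|---|---|---|
| 1-6 | 0 | 48 | 48 |
| 7 | 0 | 8 | 7 |
| 8 | 2 | 6 | 6 |
| 9 | 4 | 4 | 4 |
| 10 | 5 | 3 | 2 |
| 11 | 0 | 8 | 1 |
| 12 | 8 | 0 | - |
| 13 | 8 | 0 | - |
| 14 | 0 | 8 | 0 |
| Total | 27 | 85 | 68 |

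1. **All visits.** Home: 27/27 cells have 1 h. Site: 68/85 = 80.0% have 2 h or more, and 17/85 = 20.0% have 1 h.

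2. **By column** (site cells with 2 h or more / site cells): 6/9, 7/9, 8/10, 9/11, 8/10, 9/12, 10/12, 11/12, that is 67%, 78%, 80%, 82%, 80%, 75%, 83%, 92%. The number of patients per column is not given. If Table 2 is followed and every home option is used, the share among actual site infusions lies between 67% and 92% for any patient mix. If no home option is used, it is 68/112 = 61% over equally weighted cells.

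3. **Like period, Visits 8-14.** Site: (6 + 4 + 2 + 1 + 0)/(6 + 4 + 3 + 8 + 8) = 13/29 = 45%. Home: 0/27. At Visits 1-7 it is 55/56 site cells, with no home option.

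4. **Visit 14 PK sampling.** Protocol 8.2 has blood drawn at 1, 2, 4 and 8 h after the Visit 14 infusion in all patients. Counting that contact, the like-period site figure becomes (13 + 8)/29 = 21/29 = 72%, still against 0/27.

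5. **Share of the IRR window under scheduled observation** (infusion time + 2 h, Table 2 times, equal weights, PK contact not counted).
   - Home: 17 cells of 2 h and 10 of 3 h give 64 infusion hours. Window = 64 + 2 x 27 = 118 h; observed = 64 + 27 = 91 h; 91/118 = 77%.
   - Site: 321 infusion hours. Window = 321 + 2 x 85 = 491 h; observed = 491 - 17 = 474 h; 474/491 = 97%.

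6. **Size of the undercount: illustration only.** Understatement of home IRRs = (share of IRRs starting 1-2 h after infusion) x (share of those missed when unobserved). Neither share is in the documents. Assuming 10-30% and 25-75%, the range is 0.10 x 0.25 = 2.5% to 0.30 x 0.75 = 22.5%.

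7. **Unequal opportunity.** By column, a patient has 2-5 home-permitted infusions and 9-12 site infusions. SAP 10.2.2 specifies patients with an IRR and numbers of IRRs, with no rate per infusion.

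**The case against.** The strongest reply is that an event counts by its recorded onset time or a form tick, not by whether someone was watching. The Drug Administration form asks about events up to 24 hours. Protocol 8.3.1 requires spontaneous reports to be recorded and each subject to be questioned. When the form is completed after a home infusion is not stated, and a 1b tick made from imprecise recall could even bring an event into the window. This stands to the extent that a second-hour event at home is not automatically lost. It does not restore equal detection: reporting and timing are the steps that weaken once observation ends, and signs seen only on measurement cannot be volunteered.

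Second, the contrast is largely early against late. That is right for the 80%, but the like-period count still shows a gap.

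Third, SAP 7.4 says "No statistical tests are pre-planned in this study, which is mainly descriptive in nature", home care is not a study objective, and Home/Site is one descriptive summary. This limits the consequence, though a descriptive table can still mislead.

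Fourth, larger differences remain whatever window is used: home patients are selected as stable, and their infusions are later, shorter and fewer. This stands in full, so a 1-hour count alone would not make the comparison fair.

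Some stronger readings are tempting. A reader might infer that 80% of site infusions are observed for 2 hours; the figure counts cells of a proposed schedule, not infusions. A reader might infer that IRRs will appear to fall as infusions shorten; the SAP lists no IRR table by visit or duration. Nor can the last visits be called unobserved, given the Visit 14 PK draws.

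**Conclusion.** The point holds as one of unequal detection in a planned descriptive summary. Under Table 2, no home-permitted infusion has scheduled observation of the second hour of the IRR window, while most site cells do: 68 of 85 overall, and at Visits 8-14, 13 of 29, or 21 of 29 counting Visit 14 PK contact. Any error from lost observation can only lower the home count.

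A reader might go further and conclude that the table will favour home care by a known amount. The documents do not support that: reported events still count, no onset-time distribution is given, and the 2.5-22.5% range rests wholly on assumed shares. The counts also assume that Table 2 is followed, with its columns weighted equally. This is a cheap improvement to one table and does not affect the overall IRR result.

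**What to change.** In SAP 10.2.2 and Table 14.3.3.5.1:

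- Keep the 2-hour count by location. Beside it, add the count of IRRs with onset during the infusion or within 1 hour after its end, a window under scheduled observation in every Table 2 cell.
- Show separately the events that qualify only by a 1b tick with no onset time, since they cannot be placed in the first or second hour. Flag onsets later than the end of scheduled observation.
- Give IRRs per infusion by location, taking the denominators from the infusion counts already planned in Table 14.3.2.1, and add a row limited to Visits 8-14.
- Label the comparison descriptive, because home patients are selected as stable.

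The cost is a few SAP sentences and some extra rows, using onset times, infusion stop times and infusion counts already collected. The downside is that the 1-hour count has fewer events and depends on complete onset times. It corrects detection only; the per-infusion and Visits 8-14 rows address unequal numbers and timing, and selection can only be stated. The overall 2-hour IRR tables stay as planned, and no change to observation times or any other clinical rule is proposed.

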**Table 2: Injection Site Reaction SOC and PT Not Considered as IRR**

MedDRA SOC	MedDRA Preferred Term
General disorders and administration site conditions	Infusion site discomfort Injection site discomfort Infusion site pain Injection site pain Infusion site hematoma Injection site hematoma
Injury poisoning and procedural complications	Contusion Procedural site reaction Procedural pain
Vascular disorders	Vein rupture

The number and percentage of patients with at least one IRR and the number of IRRs will be reported in an overall table with the following parameters: Any IRR; Mild or moderate IRRs; Severe IRRs; Serious IRRs; IRRs leading to withdrawal; IRRs leading to death.

This analysis will be repeated for the following sub-groups: ADA; Gender; Previous ERT; FD classification. An additional sub-group will be the location of administration (Home or Site).

IRR summary tables by SOC and PT will present the number and percentage of subjects with at least one IRR and the number of IRRs. The tables for the IRRs will be presented overall and by severity.

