14.8 Appendix 8. Schedule of Premedication, Infusion Rates, and Observation Times Post-Infusion

Proposed schedule to:

1. Taper down premedication
2. Increase infusion rate
3. Reduce observation time after infusion

The schedule below, will guide the sites on the process to taper down premedication, increase the infusion rate up to minimal time of infusion allowed by the protocol based on the tolerability of the patient, and reduce the observation time after infusion. At the end of the process, the patient may be offered to continue therapy in a home care setup based on the Investigator evaluation and discussion with the Medical Director.

General considerations:

1. Patients whose weight is up to (\leq)100 kg, the length of first infusion will be 4.5 hours.
2. Patients whose weight is more than ($>$) 100 kg, the length of first infusion will be 6 hours.
3. Clinical follow-up (observation) after the infusion in all rates will be 4 hours for the first infusion.
4. Patients who received the previous ERT with premedication will have the first infusion of pegunigalsidase alfa with the same protocol of premedication as with the previous ERT.
5. All changes can be implemented only if there is good tolerability of the previous change.
6. In the case of questionable tolerability, the continuation of the process will be discussed between the Investigator and the Medical Director.

1. Taper down premedication

The principle in the process is:

On the first infusion: the subject will continue the premedication as in previous ERT treatment. On the next infusion, one of the medications used as premedication will be removed. If well tolerated, on the next infusion, additional medication used as premedication will be removed (when applicable). This regimen will continue up to tapering down all premedications, or best tolerability to the infusion is achieved.

2. Reduce infusion time

The principle in the process is:

Reduction in the infusion time will start after an attempt was done to taper down the premedication based on patient tolerability. The length of infusion will be reduced by 0.5 hour as described in [Table 2](#) to achieve the best tolerated infusion length or an infusion of 2 hours (for patients \leq 100 kg weight) or 3 hours (for patients weighing more than 100 kg).

3. Reduce observation time after infusion

The principle in the process is:

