| 10 | home care option | YES | YES | YES | YES | YES | NO | NO | NO |
| | infusion time | 2 H | 2 H | 2 H | 2 H | 3 H | 3 H | 3 H | 3 H |
| | observation time | 1 H | 1 H | 1 H | 1 H | 1 H | 1 H | 1 H | 2 H |
| | premedication | no premed | no premed | no premed | no premed | no premed | no premed | no premed | no premed |
| 11 | home care option | NO | NO | NO | NO | NO | NO | NO | NO |
| | infusion time | 2 H | 2 H | 2 H | 2 H | 3 H | 3 H | 3 H | 3 H |
| | observation time | 1 H | 1 H | 1 H | 1 H | 1 H | 1 H | 1 H | 1 H |
| | premedication | no premed | no premed | no premed | no premed | no premed | no premed | no premed | no premed |
| 12 | home care option | YES | YES | YES | YES | YES | YES | YES | YES |
| | infusion time | 2 H | 2 H | 2 H | 2 H | 3 H | 3 H | 3 H | 3 H |
| | observation time | 1 H | 1 H | 1 H | 1 H | 1 H | 1 H | 1 H | 1 H |
| | premedication | no premed | no premed | no premed | no premed | no premed | no premed | no premed | no premed |
| 13 | home care option | YES | YES | YES | YES | YES | YES | YES | YES |
| | infusion time | 2 H | 2 H | 2 H | 2 H | 3 H | 3 H | 3 H | 3 H |
| | observation time | 1 H | 1 H | 1 H | 1 H | 1 H | 1 H | 1 H | 1 H |
| | premedication | no premed | no premed | no premed | no premed | no premed | no premed | no premed | no premed |
| 14 | home care option | NO | NO | NO | NO | NO | NO | NO | NO |

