## 8. DEMOGRAPHICS AND BASELINE CHARACTERISTICS

### 8.1 Subject Disposition

The number and percentage of subjects who were screened, enrolled, treated, completed, and discontinued will be summarized. The documented reasons for screen failures will be tabulated. The number and percentage of subjects who discontinued will also be summarized for each reason of discontinuation. The number of subjects in each of the analysis sets will be presented. The number of patients who switched dosing regimen will be presented, as well as the number of subjects with study prolongation due to COVID-19.

The listing of disposition will indicate subjects who were affected by COVID-19. Protocol violations will be listed.

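### Infusion-related reactions by location (Home or Site) are summarised per patient and as raw counts in the SAP text available, without a link to the infusion counts by location that the SAP plans elsewhere

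*SAP*

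**What the plan says.** SAP 10.2.2 fixes the summary: "The number and percentage of patients with at least one IRR and the number of IRRs will be reported in an overall table", broken down by severity, seriousness, withdrawal and death. It is then repeated for ADA status, gender, previous ERT and FD classification, and finally by place of infusion: "An additional sub-group will be the location of administration (Home or Site"). The output is Table 14.3.3.5.1. The section gives no rate per infusion and does not say which patients form the denominator of the Home percentage.

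SAP 10.1 separately plans the number of partial or complete infusions by location, shown in Table 14.3.2.1. The text available does not connect that table to the IRR table.

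Home infusion is governed by Protocol Appendix 8. Its introduction makes it an offer made late in the course: "At the end of the process, the patient may be offered to continue therapy in a home care setup". Item 4 adds a condition: "The patients will be able to join the home care program once the patient is clinically stable with no additional changes in premedication". The speed of infusion and the length of observation must be settled as well. Table 2 marks, for each visit and for eight columns (two weight groups by number of premedications), whether home care is an option. The Visit 10 row reads "10 | home care option | YES | YES | YES | YES | YES | NO | NO | NO". The table is a proposal: "Other regimens need to be discussed and approved by the Medical Monitor/Director".

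**The concern.** The first four subgroups are patient attributes, so a percentage of patients has a fixed base in each. Location is not. One patient can have infusions in both places, in unequal numbers, and so contribute to both columns. A patient with more infusions at a place has more chances of an IRR there, and neither planned statistic takes that into account.

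The protocol builds in the imbalance: every early infusion is at site, and home care opens only in the second half of the study. The one listed table of IRRs by location would then tend to show fewer affected patients and fewer IRRs at home even if an infusion carried the same risk in either place. IRR is a listed safety endpoint, and the sample size is justified by safety evaluation, so the display should be readable without hidden arithmetic.

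**Working it through.** **Inputs from the documents**
- 14 infusions over 52 weeks, one every 4 weeks (Protocol synopsis). Check: 52/4 + 1 = 14.
- 30 patients (SAP 4.1).
- Home option by visit (Protocol Appendix 8, Table 2).

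The documents give no IRR rate per infusion. The rates of 1%, 2% and 5% below are assumptions.

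**Step 1: home visits per column.** Visits 1 to 7, 11 and 14 are NO in all eight columns. The YES cells lie at Visits 8, 9, 10, 12 and 13. Site infusions = 14 − home.

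| Column | Home option | Site, at least | Site/home |
|---|---|---|---|
| ≤100 kg, no premedication | 5 | 9 | 1.8 |
| ≤100 kg, 1 | 5 | 9 | 1.8 |
| ≤100 kg, 2 | 4 | 10 | 2.5 |
| ≤100 kg, 3 | 3 | 11 | 3.7 |
| >100 kg, no premedication | 4 | 10 | 2.5 |
| >100 kg, 1, 2 or 3 | 2 | 12 | 6.0 |

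A YES is permission, so actual home use can be lower and the ratio higher.

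**Step 2: number of IRRs.** At equal risk per infusion, expected IRRs are proportional to infusions. For patients who receive all 14 infusions under this schedule, the smallest site/home ratio is 9/5 = 1.8. With 30 patients on that split and a 2% risk: home 30 × 5 × 0.02 = 3.0, site 30 × 9 × 0.02 = 5.4.

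**Step 3: patients with at least one IRR, most balanced split (5 home, 9 site).** With the same risk p in every patient, the probability is 1 − (1 − p)^n. At p = 2%: 1 − 0.98^5 = 9.6% at home and 1 − 0.98^9 = 16.6% at site.

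If risk varies strongly between patients (assumed gamma, shape k = 0.2, each patient's risk shared across both places), the probability is 1 − (1 + np/k)^(−k). At p = 2%: 1 − 1.5^(−0.2) = 7.8% and 1 − 1.9^(−0.2) = 12.0%.

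The last columns give the probability that, among 30 such patients, home shows fewer, or more, patients with an IRR than site. The remainder is ties.

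| Model | p | Home % | Site % | P(home fewer) | P(home more) |
|---|---|---|---|---|---|
| Equal risk | 1% | 4.9 | 8.6 | 62% | 20% |
| Equal risk | 2% | 9.6 | 16.6 | 73% | 16% |
| Equal risk | 5% | 22.6 | 37.0 | 86% | 8% |
| Varying risk | 1% | 4.4 | 7.2 | 58% | 19% |
| Varying risk | 2% | 7.8 | 12.0 | 66% | 17% |
| Varying risk | 5% | 15.0 | 21.0 | 73% | 14% |

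The expected number of IRRs differs 1.8-fold under both models.

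**Step 4: effect of uptake and of the base.** Suppose half of 30 patients on the 5/9 schedule take no home infusion (assumption). Home infusions: 15 × 5 = 75. Site infusions: 15 × 9 + 15 × 14 = 345. The ratio is 345/75 = 4.6. At an equal 2% risk, 15 × 0.0961 = 1.44 patients are expected to have a home IRR. That is 9.6% of the 15 patients treated at home but 4.8% of all 30, so the unstated base alone can halve the Home figure.

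**Step 5: the same data per infusion.** IRRs per 100 infusions would be 2.0 in both places in Steps 2 and 4, as they should be at equal risk.

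**The case against.** A reader might infer that the SAP has no infusion denominator for location at all. It does: SAP 10.1 and Table 14.3.2.1 plan those counts in the same Safety population, and a reader could divide one table by the other. The gap is the missing link, not missing data. Dividing still gives only IRRs per infusion. It does not give infusions with an IRR, because one infusion can produce several. The planned exposure and IRR listings would let a determined reader reconstruct that for 30 patients, which reduces the harm further.

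A reader might also take 2 to 5 of 14 visits as a hard limit. The documents do not support that. Table 2 is a proposed regimen, others are possible with approval, a switch to infusions every two weeks changes the total, and SAP 8.1 reports "the number of subjects with study prolongation due to COVID-19". A patient who stops after Visit 13 could have 8 site and 5 home infusions, a ratio of 1.6. The distortion needs only an unequal split, not these exact figures.

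SAP 7.1 was not in the text available, and the shells are a separate document. Rows and percentage bases are often set there, so it cannot be said that the final table will lack a denominator.

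Finally, no comparison of home with site is an objective, and the SAP calls the study one "which is mainly descriptive in nature and not powered for inferential analyses". No test or interval is planned for IRRs by location. At 1% risk, only 1.5 home and 2.7 site IRRs would be expected in Step 2's setting. This limits the consequence, but the two displayed statistics would still reflect exposure as well as risk.

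**Conclusion.** The point holds as a minor one. In the SAP text available, a patient-level summary is applied to an attribute of the infusion, without a rate per infusion and without a stated base for Home. At equal risk per infusion, both statistics are expected to be lower for home.

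The size depends on the proposed schedule and on assumed risks. At least 1.8 times as many IRRs are expected at site over 14 infusions. On the most balanced split at 2%, 9.6% of patients have an IRR at home against 16.6% at site, or 7.8% against 12.0% if risk varies strongly between patients. With 30 patients, the direction in any one data set is likely but not certain. The 6-fold ratio belongs only to the three columns for more than 100 kg with premedication and should not be scaled to the trial.

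The documents do not show that home and site risks are equal, nor would a rate per infusion make the two groups comparable. Home infusions come later and only in clinically stable patients, so selection and timing remain.

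**What to change.** In SAP 10.2.2 and Table 14.3.3.5.1, show for each location:
- infusions given, taken from the Table 14.3.2.1 counts;
- infusions with at least one IRR (n, % of infusions);
- IRRs per 100 infusions.

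Base any patient percentage by location on patients with at least one infusion at that location, and print that number. Add a footnote that home infusions come later and only in clinically stable patients, so the rates correct for exposure but not for selection or timing.

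If the shells already contain these rows, a reference to them in 10.2.2 is enough. The cost is a few rows and one footnote, with no new data. The drawback is sparse counts, especially for home, so the rates should be shown beside the numbers they rest on.
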